10.3.7 Pregnancy

10.3.8 Maternal exposure

If a patient becomes pregnant during the course of the study, the IPs should be discontinued immediately.

Pregnancy itself is not regarded as an AE unless there is a suspicion that the IP under study may have interfered with the effectiveness of a contraceptive medication. Congenital abnormalities or birth defects and spontaneous miscarriages should be reported and handled as SAEs. Elective abortions without complications should not be handled as AEs. The outcome of all pregnancies (spontaneous miscarriage, elective termination, ectopic pregnancy, normal birth, or congenital abnormality) should be followed up and documented even if the patient was discontinued from the study.

If any pregnancy occurs in the course of the study, then the Investigator or other site personnel should inform the appropriate AstraZeneca representatives within 1 day, ie, immediately, but **no later than 24 hours** of when he or she becomes aware of it.

The designated AstraZeneca representative will work with the Investigator to ensure that all relevant information is provided to the AstraZeneca Patient Safety data entry site within 1 to 5 calendar days for SAEs and within 30 days for all other pregnancies.

The same timelines apply when outcome information is available.

Clinical Study Protocol

Drug Substance Durvalumab (Medi4736)

Study Number MCC 18788/MCC18788/ESR-15-11326

Edition Number 1.9.4

Date 10/08/2018

10.3.9 Paternal exposure

Male patients should refrain from fathering a child or donating sperm during the study and for 90 days after the last dose of durvalumab monotherapy.

Pregnancy of the patient's partner is not considered to be an AE. However, the outcome of all pregnancies (spontaneous miscarriage, elective termination, ectopic pregnancy, normal birth, or congenital abnormality) occurring from the date of the first dose until 90 days after the last dose should, if possible, be followed up and documented.

Where a report of pregnancy is received, prior to obtaining information about the pregnancy, the Investigator must obtain the consent of the patient's partner. Therefore, the local study team should adopt the generic ICF template in line with local procedures and submit it to the relevant Institutional Review Boards (IRBs) prior to use.

11. STATISTICAL METHODS AND SAMPLE SIZE DETERMINATION

11.1 Description of analysis sets

11.1.1 Safety analysis set

Subjects who have received at least one dose of Durvalumab will be included in the Safety Analysis Set

11.1.2 Efficacy analysis set

Subjects who have completed at least 6 treatments of every 4 week Durvalumab IV infusions and underwent the month 6 mapping biopsy will be included in the efficacy analysis set. Intention to treat analysis will be performed on all subjects who have completed at least one dose of Durvalumab and underwent the month 6 mapping biopsy.

Clinical Study Protocol

Drug Substance Durvalumab (Medi4736)

Study Number MCC 18788/MCC18788/ESR-15-11326

Edition Number 1.9.4

Date 10/08/2018

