- Compare the tumor mutation burden and alterations in DNA repair genes in the pre and post Durvalumab urothelial bladder cancer samples

Study Design:

This is a multicenter, open-label, Phase 2 study of Durvalumab to evaluate its antitumor activity for BCG refractory urothelial carcinoma in situ (CIS) of the bladder. Durvalumab will be given every 4 weeks at 1500 mg IV for total of 12 months. Cystoscopy with biopsy and TURBT (if indicated) will be performed at baseline, and every 3 months during the 12 months treatment period and then every 4 months in the 12 month surveillance period. Of note, cystoscopy at baseline, month 6, and 24 will be performed in the operating room with mapping biopsies. Patients will be off study if any of the biopsies document muscle invasive (T2 or above) urothelial carcinoma. Patients will also be off study if their month 6, 12, 16, 20, biopsies show persistent (month 6) or recurrent CIS or invasive (T1 or above) urothelial carcinoma. Otherwise, patients will remain on study until after the month 24 biopsy.

Number of Centers: 2-3 centers in North America

Number of Subjects: 34

Study Population:

Adult male or female subjects with pathologically confirmed urothelial carcinoma in situ (CIS) of the bladder that is refractory to BCG (see inclusion criteria 2).

Inclusion Criteria:

1. Age \geq 18 years at the time of screening with life expectancy of \geq 2 years
2. Must have pathologically confirmed urothelial carcinoma in situ (CIS) of the bladder that meet one of the following criteria:
 1. Persistence of high-grade CIS at 6 months following an adequate course of BCG; OR
 2. Stage/grade progression at 3 months after induction BCG; OR
 3. Recurrence of high-grade CIS after achieving a disease-free state (i.e., CR) following induction of an adequate course of BCG that occurs $<$ 9 months after the last exposure to BCG; OR
 4. Persistent CIS noted on the bladder biopsies within 3 months of completing at least 2 induction BCG (minimum of five weekly instillations).
- An adequate course of BCG should be defined as at least one course of induction (minimum of five weekly instillations) and one maintenance (two of three instillations) in a 6 months period, with an exception for any patient with grade/stage progression after induction BCG (minimum of five weekly instillations).
3. ECOG performance status of 0-1.

4. Adequate organ and marrow function, as defined as:

- Hemoglobin ≥ 9.0 g/dL,

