3. STUDY DESIGN

3.1 Overview of study design

This is a multicenter, open-label, Phase 2 study of Durvalumab to evaluate its antitumor activity for BCG refractory urothelial carcinoma in situ (CIS) of the bladder. We use a Simon's two-stage design (Simon, 1989) based on the optimal two-stage designs and admissible designs (Jung et al. 2004) for Phase II single arm clinical trials. In the first stage of this study plan, 13 patients will be accrued. If there are 3 or fewer responses in these 13 patients, the study will be stopped. Otherwise, 21 additional patients will be accrued for a total of 34. Durvalumab will be given every 4 weeks at 1500 mg IV for total of 12 months/13 doses. Cystoscopy with mapping biopsy and TURBT (if indicated) will be performed at

Clinical Study Protocol

Investigational Drug Substance: MEDI4736 Durvalumab (Medi4736)

Study Number MCC 18788/MCC18788/ESR-15-11326

Edition Number 1.9.4

Date 10/08/2018

baseline, month 6, and 24. Urine cytology with UroVysion test will be performed at baseline, month 6, and 24. Patients will be off study if any of the biopsies documented muscle invasive (T2 or above) urothelial carcinoma. Patients will also be off study if their month 6, 12, 18 biopsies showed persistent (month 6) or recurrent CIS or invasive (T1 or above) urothelial carcinoma. Otherwise, patient will remain on study until after the month 24 biopsy.

Historical controls will be used to assess the efficacy of Durvalumab. For exploratory analysis on PD-L1 expression, PD-L1 IHC will be performed with the SP263 antibody developed by Ventana. IHC positivity (either on tumor cells and/or infiltrating immune cells) will be assessed on the available mapping biopsy and or TURBT samples at time points defined in SCHEDULE OF STUDY ASSESSMENT.

Data Monitoring Committee (DMC) at Moffitt Cancer Center will monitor this phase 2 study initiated by Moffitt's investigator.

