4.4 Replacement of subjects

Subjects withdrawn from the study prior to the month 6 /week 26 mapping biopsy will be replaced to ensure total of 34 evaluable subjects. Subjects who are incorrectly enrolled but are not yet initiated on treatment should be withdrawn from the study and replaced.

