6. TREATMENT PLAN

6.1 Subject enrollment

Subjects with BCG refractory CIS urothelial carcinoma of the bladder as defined in inclusion criteria will be consented and screened.

Subjects who have completed 6 or more doses of Durvalumab and underwent month 6/week 26 bladder biopsy would be considered evaluable. Subjects who completed less than 6 doses of durvalumab will not be considered evaluable but will be followed until after the month 24 cystoscopic evaluation and biopsy. Subjects who withdrawn from the study prior to the month 6 cystoscopic evaluation and biopsy would be replaced to ensure a total of 34 evaluable subjects.

Subjects who are incorrectly enrolled but are not yet initiated on treatment should be withdrawn from the study.

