11.2.3 Interim analyses

Interim analysis of this study will be performed when 13 patients have been enrolled and completed the protocol required month 6 biopsy. If there are 3 or fewer responses in these 13 patients, the study will be stopped. Otherwise, the study will be continued and 21 additional patients will be accrued for a total of 34.

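### Every efficacy denominator, including the one called intention to treat, requires the month-6 mapping biopsy, so treated patients who leave before week 26 are not counted as non-responders

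*Combined protocol and SAP*

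**What the plan says.** Section 11.1.2 gives two efficacy sets. The main one consists of "Subjects who have completed at least 6 treatments of every 4 week Durvalumab IV infusions and underwent the month 6 mapping biopsy". The second, labelled intention to treat, is "performed on all subjects who have completed at least one dose of Durvalumab and underwent the month 6 mapping biopsy". The dose requirement differs; the biopsy requirement does not.

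The futility look follows the same pattern: "Interim analysis of this study will be performed when 13 patients have been enrolled and completed the protocol required month 6 biopsy". The stopping rule (3 or fewer responses) is then applied to those 13.

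Section 4.4 adds: "Subjects withdrawn from the study prior to the month 6 /week 26 mapping biopsy will be replaced to ensure total of 34 evaluable subjects". Section 6.1 repeats the replacement rule and defines evaluable as 6 or more doses plus the week-26 biopsy.

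Only the safety set keeps every dosed patient: "Subjects who have received at least one dose of Durvalumab will be included in the Safety Analysis Set". Section 9.1.1 defines complete response by the absence of CIS on mapping biopsies and has no rule for a missing biopsy.

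**The concern.** The plan gives treated patients two ways to miss the week-26 biopsy.

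- **Invasive disease found early.** The Synopsis states: "Patients will be off study if any of the biopsies document muscle invasive (T2 or above) urothelial carcinoma". Section 3.1 says the same. Section 9 goes further and takes patients off study for T1 or above on any biopsy. These patients are treatment failures.
- **Withdrawal of consent, loss to follow-up, or refusal of visits**, with telephone follow-up offered under Section 4.3. These patients need not be failures.

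The trial has one arm and is judged against a fixed 18%. Removing known failures from the denominator raises the reported rate, and no comparator arm is affected in the same way to offset it. Section 1.5 names progression while cystectomy is delayed as a main risk to participants, yet an early progressor would appear in neither the primary rate nor the futility count. The intention-to-treat set cannot reveal the problem because it applies the same filter.

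**Working it through.** **Inputs.** From Sections 11.2 and 11.3: p0 = 0.18, p1 = 0.40, n1 = 13, stop if ≤ 3 responses, n = 34, not pursued if ≤ 9. Section 11.2 also says to reject at 9 or more; only rejection at 10 or more reproduces the stated error, so that rule is used here. The number of leavers is not in the documents and is assumed.

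**Plan's own figures.** P(reject) = Σ over x = 4 to 13 of Bin(x; 13, p) × P(Bin(21, p) ≥ 10 − x).

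- p = 0.18: type I error 0.0473 and early stopping 0.8061, both as stated.
- p = 0.40: power 0.8031, as stated.

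**Leavers replaced.** Let k be the leavers per 34 evaluable patients, so the leave rate is q = k/(34 + k). Let a share f of leavers be certain failures and the rest respond like those who stay. If the all-treated rate is 18%, the rate among biopsied patients is 0.18/(1 − qf). The same rule is run at that rate.

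| k | q | Type I error, f = 1 | Early stopping, f = 1 | Type I error, f = 0.5 | Type I error, f = 0 |
|---|---|---|---|---|---|
| 0 | 0 | 0.047 | 0.806 | 0.047 | 0.047 |
| 1 | 2.9% | 0.056 | 0.791 | 0.051 | 0.047 |
| 2 | 5.6% | 0.065 | 0.776 | 0.056 | 0.047 |
| 4 | 10.5% | 0.087 | 0.744 | 0.064 | 0.047 |

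Worked line for k = 4, f = 1: q = 4/38 = 0.105; evaluable rate = 0.18/0.895 = 0.201; type I error 0.0871. A just-positive 10/34 (29.4%) is 10/38 (26.3%) of treated patients.

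**Failures dropped and not replaced.** With m of 34 lost, stage 1 still 13 evaluable, final n = 34 − m, and rate 0.18/(1 − m/34), the type I error is 0.049, 0.051, 0.053 and 0.054 for m = 1 to 4. For m = 4 the expected rate among the 30 left is 0.18 × 34/30 = 20.4%.

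**All dosed patients counted, no documented CR = non-response.** If 18% and 40% are all-treated rates, type I error is 0.047 and power 0.803. If they are evaluable-only rates, the all-dosed rates are p(1 − q):

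| Leavers | Type I error | Power |
|---|---|---|
| 5% | 0.035 | 0.750 |
| 10% | 0.025 | 0.686 |

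**The case against.** **The affected group may be small.** Persistent CIS at month 3 continues to the month-6 biopsy (Section 9). Patients with fewer than 6 doses are still followed with cystoscopy and biopsy (Section 6.1), and those who stop drug early but are biopsied remain in the second set. For T1 disease, Section 9.1.1 suggests that only muscle-invasive progression ends assessments, which conflicts with Section 9. All this stands and limits the expected size. It does not supply a scoring rule for those who do leave.

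**The futility count is less clear-cut than the interim section implies.** Sections 3.1 and 11.2 speak of 13 patients accrued, and Section 3.3 of the first 13, with no biopsy condition. But these sections do not say how an unbiopsied patient is scored, and the only text that sets when the look occurs requires the biopsy.

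**The design is coherent on its own scale.** It plans 34 evaluable subjects, and 0.0473 and 0.8031 are correct for evaluable subjects. The error inflation therefore depends on 18% being an all-treated rate, on leavers being disproportionately failures, and on their being replaced. Section 1.1 gives the 18% as a 3-month rate without a denominator, and the plan does not say whether going off study for progression counts as withdrawal that triggers replacement. These conditions are real, so the error figures are scenarios, not predictions.

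**A lighter remedy would be to keep the evaluable set as primary and add an all-dosed analysis.** That would at least expose the gap, but the futility and final decisions would still rest on a denominator that leaves out known failures.

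**Conclusion.** The concern holds and should be fixed. It follows from the text of 11.1.2 and the interim section without any assumption: no efficacy denominator keeps a treated patient who lacks the month-6 biopsy, and the label intention to treat is wrong for a set so defined.

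The size is conditional. With replacement and all leavers failing, leave rates of about 3% to 10% give a type I error of 0.056 to 0.087 on the all-treated scale, and early stopping under the null falls to between 0.791 and 0.744. With half of them failures the error is 0.051 to 0.064. It stays at 0.047 if leaving is unrelated to response or if 18% is an evaluable-only rate. Without replacement the error stays near nominal, but the reported rate is still inflated.

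**What to change.** - **Primary set (11.1.2 and interim section).** All subjects with at least one dose, in enrolment order: the first 13 for stage 1, then 34. Anyone without a documented CR on the week-26 mapping biopsy is a non-responder; a documented CR counts whatever the number of doses.
- **Timing of the futility look.** Once each of the first 13 dosed subjects has a week-26 result or has passed the ±14-day window.
- **Replacement (4.4 and 6.1).** Only for subjects never dosed.
- **Sensitivity and reporting.** Keep the set with 6 or more doses and a biopsy as per-protocol, and report how many treated patients had no week-26 biopsy and why.
- **Passages to reconcile.** Who goes off study before month 6 (Synopsis and 3.1 against Section 9); the month-3 biopsy (at the urologist's discretion in schedule footnote j, mandated every 3 months in 1.5); and follow-up after early drug stop (6.1 expects cystoscopy and biopsy, and 9.1.1 refers to Appendix C, whose table lists only CT or MRI as tumour assessment).

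**Cost.** Wording in four places and no more patients than planned. The reported rate will be somewhat lower, and patients who leave for reasons unrelated to response are scored as failures, which is conservative. If 40% was meant for all treated patients, no power is lost. If it was meant for evaluable patients, power is 0.750 with 5% leavers and 0.686 with 10%, so the sponsor should state which population the 18% and 40% describe.

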If the infusion takes longer than 60 minutes then blood pressure and pulse measurements should be collected every 30 minutes (±5 minutes) and as described above or more frequently if clinically indicated.

^e ECG during screening and at Day1 –baseline. There after as clinically indicated. Baseline and abnormal ECG at any time in triplicate others single. 1 ECG is needed while on treatment>>, and as clinically indicated. ECGs should be taken within an hour prior to the start of the infusion and at least one time point 0 to 3 hours after the infusion.

^f If screening laboratory assessments are performed within 3 days prior to Day 1 they do not need to be repeated at Day 1. Results for safety bloods must be available and reviewed before commencing an infusion. Gamma glutamyltransferase tested at Screening, Day 1 and as clinically indicated.

- g Free T3 and free T4 will only be measured if TSH is abnormal. They should also be measured if there is clinical suspicion of an adverse event related to the endocrine system.
- h Urinalysis performed at Screening, Day 1, every 4 weeks and as clinically indicated.
- i Coagulation tests: prothrombin time, APTT and INR – only performed at Screening and as clinically indicated.
- j Cystoscopy at baseline, week 26/month 6, and week 104/month 24 will be performed in the operating room with mapping biopsies. The mapping biopsy at baseline can be waived if the subject has a cystoscopy within 8 weeks, which documented recurrent or persistent CIS without evidence of muscle invasive urothelial bladder cancer. After month 3, 9, 12, 16 and 20 cystoscopy, a biopsy will be performed at the discretion of the Urologist.
- k Chest X-ray and CT (preferably with IV contrast) are collected during screening (for baseline) to rule out metastatic disease and secondary malignancy, Due to the low risk of metastasis with CIS of bladder, repeat imaging studies will not be indicated until cancer in the bladder has progressed to the muscle invasive stage. At this point subjects will be off study due to disease progression

Clinical Study Protocol

Investigational Drug Substance: MEDI4736 Durvalumab (Medi4736)

Study Number MCC 18788/MCC18788/ESR-15-11326

Edition Number 1.9.4

Date 10/08/2018

TABLE OF CONTENTS

PAGE

SYNOPSIS.....	3
SCHEDULE OF ASSESSMENTS.....	9
TABLE OF CONTENTS.....	13
ABBREVIATIONS AND DEFINITION OF TERMS.....	19
1. INTRODUCTION	24
1.1 Disease Background.....	24
1.2 Durvalumab Background	25

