8.1.3 End of Treatment

End of treatment is defined as the last planned dosing visit within the 12-month dosing period. For subjects who discontinue durvalumab prior to 12 months, end of treatment is considered the last visit where the decision is made to discontinue treatment. All required procedures may be completed within \pm 7 days of the end of treatment visit. <<Repeat disease assessment is not required if performed within 28 days prior to the end of treatment visit.>>

Assessments for subjects who have completed durvalumab treatment and achieved disease control, or have discontinued durvalumab due to toxicity in the absence of confirmed progressive disease are provided in APPENDIX C.

Assessments for subjects who have discontinued durvalumab treatment due to confirmed PD are presented in APPENDIX D.

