9. DISEASE EVALUATION AND METHODS

The response to immunotherapy may differ from the typical responses observed with cytotoxic chemotherapy including the following (Wolchok et al 2009, Nishino et al 2013):

- Response to immunotherapy may be delayed
- Response to immunotherapy may occur after PD by conventional criteria
- The appearance of new lesions may not represent PD with immunotherapy
- SD while on immunotherapy may be durable and represent clinical benefit.

Based on the above-described unique response to immunotherapy, subjects with persistent CIS at the month 3 bladder biopsy will continue to receive Durvalumab until the month 6 bladder biopsy documented persistent CIS or progression to the muscle invasive stage. Durvalumab will be discontinued and subjects will be off study if invasive bladder cancer (T1 or above) is documented in any of the bladder biopsies. Due to the nature of CIS of bladder, RECIST 1.1 or irRECIST will not be applicable to response assessment.

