9.1.1 Pathological response

The absence of CIS of bladder on the mapping biopsies after pathological review would be considered complete response to treatment. Subjects who are withdrawn from durvalumab treatment for reasons other than confirmed progression to the muscle invasive stage will continue to have objective tumor assessments (see Appendix C).

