APPENDIX B: DURVALUMAB DOSE CALCULATIONS

Durvalumab Dosing

The durvalumab dosing should be done depending on subject weight (if subject is < 30kg) at 20 mg/kg:

1. Cohort dose: X mg/kg
2. Subject weight: Y kg
3. Dose for subject: XY mg = X (mg/kg) × Y (kg)
4. Dose to be added into infusion bag:

Dose (mL) = XY mg / 50 (mg/mL)

where 50 mg/mL is durvalumab nominal concentration

The corresponding volume of durvalumab should be rounded to the nearest tenth mL (0.1 mL). Dose adjustments for each cycle only needed for greater than 10% change in weight.

5. The theoretical number of vials required for dose preparation is the next greatest whole number of vials from the following formula:

Number of vials = Dose (mL) / 10 (mL/vial)

Example:

1. Cohort dose: 10 mg/kg
2. Subject weight: 30 kg
3. Dose for subject: 300 mg = 10 (mg/kg) × 30 (kg)
4. Dose to be added into infusion bag:

Dose (mL) = 300 mg / 50 (mg/mL) = 6.0 mL

5. The theoretical number of vials required for dose preparation:

Number of vials = 6.0 (mL) / 10.0 (mL/vial) = 1 vials

APPENDIX C**Schedule of study procedures: follow-up for subjects who have discontinued durvalumab due to toxicity in the absence of confirmed progression of disease**

Evaluation	Time Since Last Dose of durvalumab						
	Day (± 3)		Months (± 1 week)				
	30		2	3	5	7	9
Physical examination ^a	X						
Vital signs (temperature, respiratory rate, blood pressure, pulse)	X						
Weight	X						
AE/SAE assessment	X		X	X			
Concomitant medications	X		X	X			
<<World Health Organisation>> <<ECOG>> performance status ^b	X		X	X			
Subsequent anti-cancer therapy	X		X	X	X	X	X
Survival status: phone contact with subjects who refuse to return for evaluations and agree to be contacted			X	X	X	X	X
Urine hCG or serum β hCG	X						
Hematology	X		X	X			
Serum chemistry	X		X	X			
Thyroid function tests (TSH, and fT3 and fT4) ^c	X						
Tumour assessment (CT or MRI)	At the discretion of treating physician, which is not indicated until the localized bladder cancer progressed to the muscle invasive stage (T2 or above)		X				

^a Full physical exam^b PS to be collected if available at the 2 monthly calls to obtain subsequent anti-cancer therapy and survival status^c Free T3 and free T4 will only be measured if TSH is abnormal. They should also be measured if there is clinical suspicion of an adverse event related to the endocrine system.

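### The analysis labelled intention to treat requires the month 6 mapping biopsy, so no planned efficacy set keeps every treated subject

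*Combined protocol and SAP*

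**What the plan says.** Section 11.1.2 defines two efficacy populations. The efficacy analysis set needs at least six infusions and the month 6 mapping biopsy. The ITT analysis covers "all subjects who have completed at least one dose of Durvalumab and underwent the month 6 mapping biopsy". Section 11.1.1 is the only place that takes everyone treated: "Subjects who have received at least one dose of Durvalumab will be included in the Safety Analysis Set".

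Response is defined in section 9.1.1 by the absence of CIS on the mapping biopsies. Neither that section nor section 11 says how to count a subject who has no week 26 biopsy.

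Several rules can end participation before week 26:

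- Section 3.1: "Patients will be off study if any of the biopsies documented muscle invasive (T2 or above) urothelial carcinoma". The synopsis has the same rule, and note k to the schedule of assessments says of muscle-invasive progression: "At this point subjects will be off study due to disease progression".
- Section 9 sets a lower threshold: "subjects will be off study if invasive bladder cancer (T1 or above) is documented in any of the bladder biopsies". The synopsis and section 3.1, however, apply the T1 rule only to biopsies from month 6 onward.
- Note j leaves the biopsy at the month 3 cystoscopy to the urologist's discretion.

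Sections 4.4 and 6.1 replace subjects withdrawn before the week 26 biopsy, so that 34 evaluable subjects are reached. Section 11.2.2 makes the efficacy reporting descriptive.

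**The concern.** An ITT analysis in a single-arm trial exists to show the response rate among everyone who started treatment, including those the evaluable set leaves out. Here it relaxes the dose requirement but keeps the biopsy requirement, so it is still conditioned on the outcome having been measured.

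The loss need not be random. Invasive progression before month 6 is treatment failure, and it is also a reason for having no week 26 biopsy. Section 1.5 itself recognises that delaying cystectomy in a non-responder can allow progression to the muscle-invasive stage. Because withdrawn subjects are replaced, a final count of 34 evaluable subjects would not show how many had been lost.

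At stake is how the reported ITT rate is read against the 40% in the primary objective. A reader would take it as the rate among all treated subjects, which it is not.

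**Working it through.** **The plan's own figures.** The plan gives no figure for the ITT set. The figures in section 11.2 belong to the two-stage rule and can be checked exactly: stop if 3 or fewer of 13 respond; succeed if 10 or more of 34 respond.

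- Early stopping at 18%: P(X ≤ 3), X ~ Bin(13, 0.18) = 0.8061.
- Success probability: sum over x = 4 to 13 of P(X = x) × P(Y ≥ 10 − x), Y ~ Bin(21, p). This gives 0.0473 at p = 0.18 and 0.8031 at p = 0.40.
- Expected size at 18%: 13 + (1 − 0.8061) × 21 = 17.07.

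All four match the design table, and none of them uses the ITT set.

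**Following one subject through the rules.** The month 3 cystoscopy is at week 14 ± 14 days, so weeks 12 to 16. Doses fall at weeks 0, 4, 8, 12 and 16. The subject has had 4 doses by week 14, 5 by week 16 if that dose is given, or 3 if a week 12 biopsy precedes the week 12 dose. Suppose a biopsy is taken and shows T2 or above.

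1. Six-dose efficacy set: not met (3 to 5 doses, no week 26 biopsy).
2. ITT set: dose condition met, biopsy condition not met.
3. Safety set: included.

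The subject is a known failure and appears in no efficacy denominator. A treated subject who withdraws or is lost before week 26 is left out in the same way, though that subject's response is unknown.

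**Size.** Let n be treated subjects with the week 26 biopsy (any number of doses), m treated subjects without it, and x responders. Count the m as non-responders.

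- Rate as written: x/n. All-treated rate: x/(n + m).
- Relative excess: (x/n) ÷ (x/(n + m)) − 1 = m/n, for x > 0.

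The documents do not give m; 1 to 5 is assumed. The ITT set can exceed 34, because it also admits biopsied subjects with fewer than six doses, so n = 34 to 37 is assumed. The relative excess then runs from 1/37 = 2.7% to 5/34 = 14.7%.

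| Case | As written | All treated |
|---|---|---|
| m = 1 | 14/35 = 40.0% | 14/36 = 38.9% |
| m = 3 | 14/35 = 40.0% | 14/38 = 36.8% |
| m = 5 | 14/35 = 40.0% | 14/40 = 35.0% |
| Stopped at stage 1, m = 1 | 3/13 = 23.1% | 3/14 = 21.4% |
| Stopped at stage 1, m = 2 | 3/13 = 23.1% | 3/15 = 20.0% |

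With m = 0 the two rates are identical.

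**The case against.** The strongest reply is that nothing is decided on this analysis. The go/no-go rule in sections 11.2 and 11.3 works on response counts, with evaluability set in section 6.1, and an evaluable-subject primary analysis is ordinary in phase 2. The ITT rate carries no threshold or test. That stands, and it limits the point to one descriptive percentage.

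The month 3 route is also conditional. A biopsy must be taken at the urologist's discretion and must show invasion. For T1 disease at month 3 the documents conflict, so only T2 or above is a settled example. That stands too. It makes the number affected uncertain but does not restore anyone to the set.

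Finally, m is likely to be limited. Section 6.1 follows subjects with fewer than six doses through the month 24 cystoscopy and biopsy, and section 9.1.1 continues assessments after stopping drug for reasons other than muscle-invasive progression. Subjects who stop for toxicity should therefore reach week 26 and enter the ITT set. A reader might infer the opposite from Appendix C, which has no cystoscopy or biopsy row. The documents do not support that: section 6.1 and note j keep the biopsies in place, and Appendix C does not cancel the main schedule.

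**Conclusion.** The point holds in a limited form. The set called ITT is conditioned on the endpoint being observed, and no planned efficacy set retains all treated subjects. A subject found with T2 or above before month 6 is dropped as a known failure; those lost or withdrawn before week 26 are dropped with response unknown.

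The absolute effect in the 40% example is 1.1 points at m = 1 (40.0 − 38.9) and 5.0 points at m = 5 (40.0 − 35.0). It rests on an assumed m, on those subjects being non-responders, and on at least one responder in the set. It may be zero.

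A reader might go further and infer that dropping and replacing early failures inflates the type I error of the trial's decision. The documents do not support that as part of this point. The stated 0.0473 is the error of a rule applied to the subjects counted, the ITT analysis does not enter that rule, and any inflation measured on an all-treated basis would need a share without biopsy that the plan does not give. Nor can it be said that every early progressor is removed, since the month 3 biopsy is discretionary.

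**What to change.** In section 11.1.2, define the ITT set as all subjects who received at least one dose of durvalumab, the same subjects as the safety set in section 11.1.1. Count a missing week 26 mapping biopsy as non-response. Report how many are missing and why, separating invasive progression from withdrawal, loss to follow-up and missed procedures. Keep the present biopsied-only rate as a labelled sensitivity analysis.

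The cost is wording: no added procedure, no extra subjects, and no change to the six-dose evaluable set or the two-stage rule. The downside is that the ITT rate may be slightly lower and a biopsy missed for an unrelated reason will count as non-response. The listed reasons and the sensitivity rate let a reader see how far that matters.
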